## SYNOPSIS

Title	Testing a system for near real-time monitoring on vaccination coverage, benefits and risks in Europe with acellular pertussis-containing vaccines as a test case.
Medicinal product	Any acellular pertussis-containing vaccine that was available during the study period and used in the study population in the 4 countries participating to the current study (Italy, UK, Spain and Denmark).
Product reference	Acellular pertussis-containing vaccines.
Research question and objectives	
The overall objective of the ADVANCE Proof of Concept (POC) studies is to build and test a system (including testing data availability) for benefit-risk monitoring of vaccines in Europe. Specifically, the objective of POC1.2 is to establish the feasibility of continuously and rapidly updating the information on coverage, benefits and risks using electronic healthcare and surveillance databases, while visualizing these data using a dashboard.
 
The overall objective is:
 
Building the capacity for near real-time monitoring in Europe.
 
The specific objectives are to:
 
 
1. Evaluate the ability of databases to generate periodic data with limited latency to secure near real-time monitoring on a preferably weekly basis (or bi-weekly/monthly if weekly would not be feasible)
 
2. Visually monitor vaccination coverage, benefits and risks using an interactive dashboard
 

Data sources	The potential data sources will include, Asl Cremona (ASLCR), Regional Database Tuscany (ARS) and PEDIANET from Italy; SIDIAP from Spain; RCGP from UK and SSI/AUH from Denmark.
Investigators and main authors	
POC1.2 study team:
 
Principal investigators (PIs) of POC1 will also act as PIs of POC1.2: [name] (benefit-risk), [name] (Risk), [name] (Coverage), [name] (Benefit)
 
[name] (study statistician), [name] (study statistician), [name] (study manager), [name] (expert pharmacoepidemiologist), [name] (WP5 lead, epidemiologist), [name] (WP5 lead, pharmaco-epidemiologist).

Disclaimer	The study described in this protocol is conducted as part of the IMI ADVANCE project with the aim to test methodological aspects of the

---

	
design, conduct and reporting of studies for vaccine benefit-risk monitoring activities. The protocol presented herein relates solely to the testing of these methodologies and is not intended to inform regulatory or clinical decisions on the benefits and risks of the exposures under investigation. Therefore any use of information from these studies should carry over this warning and be used accordingly.

--	---

## LIST OF ABBREVIATIONS

ADVANCE	Accelerated Development of VAccine beNefit-risk Collaboration in Europe
aP	acellular (pertussis vaccine)
B/R	Benefit/ Risk
CDM	common data model
DLP	data lock point
EU	European Union
GPP	good participatory practice
GVP	good pharmacovigilance practices
HHE	hypotonic-hyporesponsive episode
ICD	International Classification of Diseases
ICSR	individual case safety reports
IEC	independent ethics committee
IMI	Innovative Medicines Initiative
IRB	institutional review board
MAH	marketing authorisation holder
PAS	post-authorization study
PASS	post-authorization safety study
POC	proof-of-concept
REB	research ethics board
SAP	statistical analysis plan
SC	steering committee
STROBE	STrengthening the Reporting of OBservational studies in Epidemiology
wP	whole-cell pertussis (vaccine)
WP	work package (i.e. WP4 or WP5)

---

## 1.2. Principal Investigators

This study is a continuation of the first proof of concept (POC) study on pertussis vaccination for which different principal investigators led the study teams on the coverage, benefit and risk studies and evidence synthesis study (benefit-risk). For the current POC study (POC1.2), the same processes as in the POC 1 will be followed, however, this time we will do near real-time monitoring, whereas POC1 was a retrospective cohort study. As such, the same PIs will work together on the POC1.2 coordination team.

#### **DATABASE LIAISONS/CUSTODIANS**

Databases will participate upon demonstration of data quality in the quality assessment module (see also Appendix 1) and when having the ability to generate periodic data, with a target of weekly refresh of data less than a week old (bi-weekly/monthly will also be accepted). Previous quality assessments conducted as part of POC1 remain valid. Custodians of contributing databases will be members of the study team if they meet the requirements and conditions from the ADVANCE Code-of-Conduct.

---

## 2. ABSTRACT

Date of protocol abstract: December 11, 2017
Title: Testing a system for near real-time monitoring of vaccination coverage, benefits and risks in Europe with pertussis vaccines as a test case.
Rationale and Background: POC1.2 aims to test near real-time and visual monitoring of coverage, benefits and risks of acellular pertussis (aP) vaccination. POC1.2 is designed as a continuation of POC1 to leverage previously completed work. POC1.2 will use near real-time visual monitoring of aP vaccines in Europe as a test case, aiming to mimic the introduction of a new vaccine. The interactive dashboard developed as an additional analysis to POC1 will be regularly updated for monitoring.
Research Question and Objectives: The overall objective of the ADVANCE POC studies is to build and test a system (including data availability) for the benefit-risk monitoring of vaccines in Europe. The objective of POC1.2 is to determine the feasibility of periodic and rapid assessments of vaccine coverage, benefits and risks using electronic healthcare databases, while displaying these data using a dashboard. The specific objectives are to: 

1. Evaluate the ability of databases to generate periodic data with limited latency to secure near real-time monitoring on a preferably weekly basis (or bi-weekly/monthly if weekly would not be feasible)

2. Visually monitor vaccination coverage, benefits and risks using an interactive dashboard

Target Population: All children from their start of follow-up in the database until school-entry pertussis booster, 6 years of age or any periodic data lock point within the eligible ADVANCE databases.
Observation Period: The total observation period consists of two distinct periods. The first period starts from 01 January 2014 until the start of the near real-time monitoring upon approval of the protocol and has as objective to establish a baseline. The start of the first period (01 January 2014) was chosen to balance data accuracy and computational burden. The second period has the objective of near real-time monitoring and will cover a few months. This period will start upon protocol approval until last periodic data lock point (DLP) (i.e. the time the last periodic database extract is produced) and will cover a few months.
Study design: A dynamic cohort study
Exposure The exposure of interest is vaccination with any acellular pertussis-containing (aP) vaccine recorded in the study population covered by the ADVANCE databases participating in POC1.2
Outcomes

The risk outcomes are hypotonic hypo-responsive episodes (HHE), febrile convulsions/seizures, fever, somnolence and persistent crying. The benefit outcome is the vaccine preventable disease (here: pertussis, confirmed or probable).

#### **Data analyses**

The test case is near real-time (weekly or bi-weekly/monthly, depending on the database) visual monitoring of vaccination coverage, benefits and risks of pertussis vaccination. The monitoring will be facilitated through the use of an interactive dashboard developed based on the POC1 data. The dashboard contains three monitoring tabs with visualizations:

- Coverage: number of administered doses per week over calendar time (extrapolated to the population of interest) and vaccination coverage (%) within specific age groups by calendar time
- Benefits: observed pertussis incidence in the total population by calendar time
- Risks: incidence rates in event specific risk windows and in control periods (out of risk windows) at vaccination eligible ages, separately for each risk outcome by dose, estimated cumulatively over calendar time.

#### **Data Sources:**

The potential data sources were selected from all databases available from ADVANCE partners and associated partners, based on the following eligibility criteria:

- Successful database quality assessment based on database fingerprinting and benchmarking for the events and vaccine of interest
- Theoretical ability to generate periodic data, with a target of weekly refresh of data, as recovered based on a detailed survey

Based on these two criteria the following six data sources remained: ASLCR, ARS, PEDIANET, RCGP, SIDIANP and SSI/AUH.

#### **Sample size:**

Entire eligible study population from the six eligible databases.

#### **Informed Consent and Ethical Approval:**

This analysis will be conducted on the basis of secondary use of data from ADVANCE partners and associate partners. Each contributing database will follow local governance and privacy rules prior to sharing anonymized data.

#### **Disclaimer**

The study described in this protocol is conducted as part of the IMI ADVANCE project with the aim to test methodological aspects of the design, conduct and reporting of studies for vaccine benefit-risk monitoring activities. The protocol presented herein relates solely to the testing of these methodologies and is not intended to inform regulatory or clinical decisions on the benefits and risks of the exposures under investigation. Therefore any use of information from these studies should carry over this warning and be used accordingly.

---

### 3. AMENDMENTS AND UPDATES

Protocol amendments following IRB approval of the local databases:

**Table 1 Overview of Protocol Amendments and Updates**

	Date (DDMMYY)	Section of the study protocol	Amendment or update	Reason
1	16/03/2018	Section 7.2.9.3	Aggregated data will not be sent to RRE anymore for post-processing, but transformed to its most aggregate level locally and then immediately transferred to the P-95 dashboard server. This step now avoids use of the RREm with full backend (local) data transformation. Figure 2 shows the process.	Due to a recent move of office, P95 lost its fixed IP-address, which is needed to access the RRE. Getting a fixed IP-address from the internet provider takes much longer than anticipated. Avoiding the RRE will reduce delays
2				
....				

---

#### 4. MILESTONES

**Table 2: Overview of Study Milestones**

Activity	Due date
Submission protocol to ADVANCE steering committee (SC)	Dec 15, 2017
Comments from SC	January 5, 2017
Submission to Ethics Committee/Institutional Review Board	January 16, 2017
Protocol approval Ethics Committee/Institutional Review Board	February 28, 2018
Statistical Analysis Plan (SAP)	January 24, 2018
Review SAP	January 31, 2018
Final SAP	February 5, 2018
Near real-time monitoring (3 months)	March – April, 2018
Draft report version 1	May 18, 2018
Study team review report version 1	May 25, 2018
Report version 2	May 30, 2018
SC and ADVANCE consortium review report version 2	June 15, 2018
Rebuttal and final report submitted to IMI	June 30, 2018

---

---

## 5. RATIONALE AND BACKGROUND

At the core of the mission of ADVANCE and many of its stakeholders is the concept of vaccine Benefit/Risk (B/R) monitoring. Monitoring should be understood as a periodic assessment of several key parameters including, coverage, incidence of adverse events, and incidence of the vaccine preventable disease to trigger an alert if and when there is an indication that the B/R profile in the population is different from what is expected (based on clinical trials, observational studies or similar products). This alert would generate a subsequent and possibly more formal assessment and analysis of the vaccine. Monitoring should, in principle, start as soon as a new vaccine is introduced in a given country and continue throughout the vaccine's lifecycle, and would also be applied to vaccines with established B/R profiles.

B/R monitoring requires information that is available in a timely fashion. Hence, the goal is to have access to near real-time information, which is defined as either weekly or monthly refresh of data that is only a few days old. Weekly periodicity is preferred and has been previously successfully implemented for influenza vaccine monitoring (H1N1 pandemic). It is also the approach used for the VSD rapid cycle analyses and used in some published studies [1, 2]. Weekly monitoring has also been recommended in a recent EMA guidance for seasonal influenza vaccine safety monitoring.

Visual monitoring of the component parameters of B/R as well as two composite B/R measures has been recently prototyped in a dashboard using simulated data on rotavirus (<http://apps.p-95.com/BRMonitor/>). This approach was found useful and informative. Subsequently, the dashboard was further developed to incorporate the retrospective real world data on pertussis from the first proof of concept study (POC1), demonstrating good acceptability.

POC1 is the first ADVANCE POC study. The overall objective of POC1 is to develop and test the ability of the currently available ADVANCE system to perform post-marketing studies of the benefits and risks of vaccination in Europe. Pertussis vaccination, notably comparing the benefits and risks of whole-cell pertussis (wP) vaccinations with aP vaccinations, was chosen as the first test case. The POC1 study is completed and is extensively described in ADVANCE deliverable D5.6. (Accessible at the ADVANCE Members area: <http://www.advance-vaccines.eu/>).

The current POC, POC1.2, will be a real-world test case of near real-time visual monitoring of coverage, benefits and risks using electronic healthcare data. POC1.2 will be designed as a continuation of POC1 to maximally leverage previous work. The dashboard developed as additional analyses to POC1 and described above will be used for monitoring.

---

The expected learnings from POC1.2 include:

1. Identifying databases with proven fast and frequent data refresh that can be used for near real time monitoring of vaccination coverage, benefits and risks rates (on top of the theoretical ability as identified based on a survey), and understanding the reasons, if any, why some databases cannot be used for monitoring.
2. Testing the requirements for data flow and data processing to ensure near real-time monitoring;
3. Using a dashboard for near real-time monitoring.

## **6. RESEARCH QUESTION AND OBJECTIVES**

The overall objective of POC1.2 is to determine the feasibility of periodic and rapid assessments of vaccine coverage, benefits and risks using electronic healthcare databases.

The specific objectives include:

1. Evaluate the ability of databases to generate periodic data with limited latency to secure near real-time monitoring on a preferably weekly basis (or bi-weekly/monthly if weekly would not be feasible)
2. Visually monitor vaccination coverage, benefits and risks using an interactive dashboard

The test case will be the monitoring of acellular pertussis vaccination in Europe, mimicking the launch of a new vaccine.

## **7. RESEARCH METHODS**

### **7.1. System testing: measures of success**

The following criteria will guide the measurement of the level of success of POC1.2:

- **1. Feasibility:** at least 3 databases (i.e. 50% of the pre-identified databases) can provide data on coverage, benefits and risks for near real-time monitoring (meeting criteria 2 and 3 below) to demonstrate the feasibility of vaccine benefit-risk monitoring in Europe.
- **2. Frequent refresh rates:** at least 3 databases can provide weekly (most successful), bi-weekly (highly successful) or monthly (successful) data on coverage, benefits and risks.
- **3. Timeliness:** at least 3 databases can provide data of 1 week (most successful), 2 weeks (highly successful), 1 month (moderately successful) or 2 months (minimally successful) old. The timeliness of the monitoring will be based on the distribution of the 'reporting delays': time between event date

---

and dashboard system date (i.e. date when new events that happen during the monitoring phase are displayed for the first time on the dashboard).

- 4. Acceptability of the approach by all ADVANCE stakeholders: the link to the monitoring dashboard will be shared with all ADVANCE stakeholders. A semi-structured survey and discussions will be organised to collect feedback. The ADVANCE consortium and the scientific advisory board (see section 7.2.10.2) will discuss and judge the successfulness of the POC1.2 study, discussing strengths, limitations and areas for further improvement.

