### **7.2.5. Study Period**

The study period will consist of two distinct periods. The first period will start from 01 January 2014 until the start of the near real-time monitoring and has as objective to establish a baseline. The second period is the actual near real-time monitoring which will start upon approval of the protocol by the institutional review board/independent ethics committee/research ethics board (IRB/IEC/REB). The period of near real-time monitoring will cover a minimum of 3 data loads and be maximum 3 months long.

It should be noted that the start of follow-up for the POC1.2 study period is arbitrary and was selected to ensure an observation period long enough to obtain stable rates while also minimizing the computational burden. This arbitrary date does not correspond in any way to a date where there would be a need or a trigger to start monitoring (as in normal use of a monitoring system). The same principles apply to the date that will be used for the start of the short period of near real time monitoring.

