### **7.2.7.2. Reporting delays**

Timeliness is essential for monitoring. Therefore, we will study delays in reporting by comparing event dates with the date the event is first used in the dashboard for monitoring. The analysis will be restricted to events for which it is known when they were first used (i.e. events that are present in the updated dashboard at time  $I$ , but were not in the previous update at time  $I-1$ ). The distribution of reporting delays will be obtained by event type or group of events (events recorded at hospital vs. primary care; exposure events, health outcome events) and will be summarized using measures of central tendency (average or median, whichever is most appropriate) and measures of spread (standard deviation or inter-percentile ranges, whichever is most appropriate).

As the total reporting delay is an accumulation of time lost due the processes at the level of the healthcare system (e.g. the time it takes for hospitals to report back to the GP - healthcare level) and processes at the level of the databases (database level) we will also look at the time between the most recent end of follow-up dates in the population CDM files and the use of this data in the dashboard. This will inform us regarding the amount of delays at the database level.

[figure not shown]
This way, we will obtain the total reporting delays as well as the delays at database level, allowing us to derive the delays at healthcare level.

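### Criterion 3 in Section 7.1 ties reporting delay to events occurring in the monitoring phase, which conflicts with Section 7.2.7.2 and, read as written, biases delays downward

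*Protocol*

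**What the plan says.** Protocol Section 7.1, criterion 3, asks that at least 3 databases deliver sufficiently recent data. The grades run from 1 week down to "1 month (moderately successful) or 2 months (minimally successful) old", so anything older than 2 months earns no grade. Delay is the time from the event date to the dashboard date, and the latter is explained as the "date when new events that happen during the monitoring phase are displayed for the first time on the dashboard". Criterion 1 (feasibility) requires criteria 2 and 3 to be met.

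Section 7.2.7.2 describes the delay analysis: "The analysis will be restricted to events for which it is known when they were first used". It explains this as events in the current update that were absent from the one before, and sets no condition on when the event occurred. The summary is the "average or median, whichever is most appropriate", with a measure of spread. It adds a database-level delay: the "time between the most recent end of follow-up dates in the population CDM files and the use of this data in the dashboard".

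On phase length, Section 7.2.5 states: "The period of near real-time monitoring will cover a minimum of 3 data loads and be maximum 3 months long". The row in Table 2 begins "Near real-time monitoring (3 months" but is scheduled for "March – April, 2018", which is 31 + 30 = 61 days.

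**The concern.** If an event must both occur and be displayed within the phase, it counts only when event date plus delay falls on or before the last load. Long delays are then lost selectively, and no delay longer than the phase can be recorded. An event late in the phase contributes only if it was reported quickly. The slowest databases gain most, and they are the ones a timeliness criterion should identify. Because criterion 3 feeds criterion 1, the bias could reach the study's overall feasibility conclusion.

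Long delays are realistic here. In Section 7.2.3 the Danish patient registry, which supplies the Danish events, is described as up to 3 months behind.

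**Working it through.** The protocol gives no expected delay for this criterion, so there is no figure to reproduce.

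**Inputs from the protocol.** Thresholds of 7, 14, 30.4 and 60.9 days (1 week, 2 weeks, 1 month, 2 months); phase of 61 days (Table 2 dates) or 91 days (3-month maximum); weekly or monthly loads.

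**Assumptions.** Constant event occurrence; a baseline load at day 0; the median as the graded statistic; and the delay distribution, for which a range is shown. With weekly loads the last one in a 61-day phase falls on day 56 (8 × 7); in a 91-day phase it falls on day 91 (13 × 7).

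**Formula.** Let *f(d)* be the true density of the delay until the record is available, and *L* the day of the last load. Under the 7.1 wording the observed density is proportional to *f(d)(L − d)* for 0 ≤ *d* ≤ *L*. Waiting for the next weekly load adds 3.5 days on average.

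**Uniform delays, 0-91 days** (one reading of the Danish registry's lag). Here *f* is constant, so the truncated median is *L*(1 − 1/√2) = 0.293 *L*.
- True median at display: 45.5 + 3.5 = 49 days.
- 61-day phase: 0.293 × 56 = 16.4; plus 3.5 gives 20 days.
- 91-day phase: 0.293 × 91 = 26.7; plus 3.5 gives 30 days.

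Simulation with explicit load dates gives the same 49, 20 and 30 days. The grade moves from the 2-month to the 1-month category, only just so in the 91-day phase.

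**Delays with a true median of 75 days, weekly loads** (simulation; 78-79 days at display, so no grade is deserved):

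| Assumed shape | 7.1 sample, 61-day phase | 7.1 sample, 91-day phase |
|---|---|---|
| Exponential | 18 d | 25 d |
| Gamma, shape 2 | 27 d | 38 d |
| Gamma, shape 4 | 36 d | 49 d |
| Lognormal, log-SD 0.5 | 40 d | 52 d |

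Every cell earns the 1-month or 2-month grade. The more concentrated the delays, the smaller the bias. With monthly loads the true median at display is about 91 days. The exponential, gamma shape 4 and lognormal cases then appear as 29-51 days (61-day phase) or 37-61 days (91-day phase), the last value sitting at the 2-month limit.

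**All delays between 2 and 3 months.** For delays uniform over that range, a 61-day phase displays no phase events, so no delay can be computed. A 91-day phase gives a median of 73 days (weekly loads) or 82 days (monthly), above 2 months. Fixed delays of 65, 75 or 90 days behave the same way, with 91-day-phase medians of 68-91 days.

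**The 7.2.7.2 sample.** In every scenario its median agreed with the true median at display to within about a day: 49 days for the uniform case, and 78-79 (weekly) or 90-91 (monthly) for the 75-day cases. This holds under stable incidence and without bulk backfill.

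**The case against.** The strongest reply is that the disputed words only explain what the dashboard date is and do not define an analysis set. The section on reporting delays does define one, and it is not truncated. It also adds a database-level delay that does not depend on event dates. This stands to the extent that a reader cannot infer from 7.1 that the protocol as a whole measures delay only on phase events. It does not remove the conflict, because the narrower wording sits in the section that sets the success criterion.

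A reader might also infer that any database with delays of 2-3 months will be graded timely. The calculation does not support that: if all delays lie in that range, the result is no events or a median above 2 months. A false grade needs a wide spread of delays, and the protocol does not state the spread.

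A third inference is that criterion 3 cannot fail. That would follow only for a database with at least one displayed phase event in a 61-day phase. The 61 days come from a milestone row that contradicts its own label, in a table with other apparent date slips (two January 2017 steps follow one in December 2017). Section 7.2.5 sets a 3-month maximum, under which delays of 2-3 months can be seen for early events.

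Section 7.2.8 concedes that the phase may be too short for full system testing, but it does not mention truncated delays. The criteria guide a judgement by the consortium and its advisory board and are not a formal test, which softens the consequence. Finally, the wider sample has its own weakness. Pedianet is still linking birth cohorts to a vaccination register (Section 7.2.3), so old records could arrive in bulk with delays that reflect linkage and not reporting.

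**Conclusion.** The point holds as a conflict between Sections 7.1 and 7.2.7.2 in which the 7.1 wording, taken literally, biases delays downward and can change a grade. With weekly loads, a true 49 days at display is seen as 20 or 30 days under uniform 0-91 day delays. A true 79 days is seen as 27 or 38 days under the gamma shape 2 assumption, which turns no grade into a success grade. These figures rest on assumed delay shapes, constant event occurrence and grading by the median; they illustrate the mechanism and do not predict any named database's result. The bias is largest when delays are widely spread, and no false grade arises when all of them lie between 2 and 3 months. The mismatch in Table 2 is a smaller matter, but it determines where truncation falls.

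**What to change.** 1. In Section 7.1, remove the clause that limits events to those occurring in the phase, and refer to the Section 7.2.7.2 sample: all events first displayed between consecutive updates, whatever their event date within the study period. Report bulk backfill, such as newly linked cohorts, separately.
2. Alternatively, keep the 7.1 sample, estimate the delay distribution with a right-truncation (reverse-time) estimator, and state that delays beyond the phase length cannot be estimated.
3. If phase events are used for grading, state that a database with none displayed does not meet criterion 3.
4. Reconcile the 3-month label in Table 2 with its March-April dates and with the maximum in Section 7.2.5.

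The cost is a few sentences, one milestone date and a little extra analysis. No new data are needed, since the study period already starts on 01 January 2014. Some databases may receive less favourable grades.
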